7. SAFETY ASSESSMENTS

Participant safety will be monitored once an individual is enrolled in the study. Since our institutional IRB has deemed our TARA intervention to be very minimal risk, we do not anticipate any significant adverse experiences from our TARA intervention. However, to assure comprehensive review of potential safety events, we have included the following alphabetical list of expected adverse experiences for the TARA study intervention, criteria for management and modification of the TARA study intervention regimen or participant assessments if an adverse event occurs:

- 1. Experiencing difficult emotions such as sadness or anger during some of the TARA intervention class activities or home assignments. If participants experience difficult emotions, they can stop the activity and speak to the class leader or study staff. The class leader will talk about how to handle difficult emotions that come up during home assignments at the first class, and throughout the course as needed.
- 2. Restlessness. If participants experience restlessness, they can stop the activity and speak to the class leader or study staff. The class leader will talk about how to handle restlessness that come up during home assignments at the first class, and throughout the course as needed.

If an adverse event occurs, the AE will be assessed by [name] (medical director and co-PI) and recorded in the Adverse Event form (please see Adverse Event form in the Appendix).

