7.2 Methods and Timing for Assessing, Recording, and Analyzing Safety Parameters

The risk profile of our study intervention (TARA) is very minimal. Our institutional IRB has deemed our TARA study intervention to be very minimal risk. Our published peer-reviewed paper using our TARA study intervention in depressed adolescents also demonstrates the exceptional safety and very minimal risk of our TARA study intervention (Henje [name] et al., 2017). The Methods and Timing for Assessing, Recording, and Analyzing Safety Parameters are as follows: (1) At each of the 12 study TARA intervention visits (i.e., TARA visits 1 through 12 [Study visits 2 to 13] as detailed above in section 6.1: Schedule of Evaluations), any and all adverse events will be collected and recorded using the Adverse Event form. Any Adverse Event(s) will be reviewed by the PIs and a determination of the relationship of the Adverse Event to the TARA study intervention will be made by the medical PI ([name]). Based on the study intervention relationship to the Adverse Event as determined by [name] and the severity of the Adverse Event, [name] and [name] will decide upon the appropriate action to take regarding the study intervention (TARA).

If the Adverse Event is classified as Serious Adverse Events, the Serious Adverse Event form will be filled out.

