9.4 Interim Analyses and Stopping Rules

This trial will not have any interim analyses. It is itself a preliminary study which will lead to a decision about whether a follow-on study will be conducted in depressed adolescent volunteers.

Safety findings that will trigger a safety review: If 15% of the enrolled study participants experience a Grade 2 (moderate) or Grade 3 (severe) adverse event (AE) related to the TARA study intervention, then a safety review will occur.

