9.5.2 Secondary Outcomes

The secondary outcomes include the following:

Emotional Problems. Emotional problems will be assessed by the SDQ questionnaire comparing the value before randomization (Visit 1) to the one 12 weeks

after randomization (Visit 14).

Other outcomes

Adherence. The proportion of volunteer randomized to TARA training who participate in at least 75% of the sessions. We expect that at least 80% of participants on the TARA arm will attain this level of adherence.

Safety and tolerability of the intervention. Adverse events will be collected at each visit and graded, and their attribution to their participation will be assessed. The safety of the TARA intervention will be demonstrated if < 15% of the participants experience a grade 2 (moderate) or grade 3 (severe) adverse event related to the TARA intervention.

To demonstrate the tolerability of the intervention used in this study, we will use the Child Session Rating Scale (CSRS) score. The CSRS is a 4-item self-assessments using a 10-cm visual analog scale (Campbell & Hemsley, 2011), with higher scores indicating better experience. This measure of tolerability will be completed after each session. Participants will rate the session in terms of how much they felt listened to, how important the content and activities were to them, how much they liked the session, and their overall experience. The intervention will be tolerable if the median CSRR is at least 20 in >80% of participants.

Retention. To demonstrate the ability to retain subjects, we will retain at least 80% of randomized participants for primary outcome measurement at the end of the study regardless of adherence to the intervention.

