Emotional Problems. Our hypothesis is that training will improve emotional problems as assessed by the SDQ T-score compared with controls. We will use an analysis of covariance (ANCOVA) accounting for sex and fit by maximum likelihood. Stata (College Station, TX) will be used to perform data analyses. We will additionally explore age, pubertal status (as determined by the Tanner stage self-report form (Tanner et al., 1962)), and pre-training associations with the changes through an examination of interaction. Potential pre-/post-training differences in movement during MRI will be accounted for by assessing the number of rejected diffusion directions. Sex as a biological variable: In all analyses described, sex will be included as a factor, we will also test for a randomized arm by sex interaction.

In addition, we will examine relationship between changes in node strength of the putamen and changes in emotion by performing a Spearman rank correlation change in node strength through 12 weeks with change in SDQ through 12 weeks.

Other outcomes.

Adherence. We summarize adherence to training including (i) tabulating the number of participants on the training arm who complete at least 75% of sessions, (ii) calculate the minimum, maximum, median and interquartile range of sessions attended by those randomized to the TARA training arm.

Safety and tolerability of the intervention. Adverse events of grade 2 or higher will be tabulated between the arms and compared by the Fisher exact test. Tolerance scores on the CSRS will be summarized (minimum, maximum, median, interquartile range) at each study visiting on the TARA training arm.

We will tabulate the proportion of participants who are retained through 12 weeks and complete the MRI exam and SDQ questionnaire. These will be compared between the arms by the Fisher exact test.

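### Section 9.6 tabulates adverse events only from grade 2 upwards and specifies no summary by event type, so recorded mild cases of the two harms expected from TARA appear in no planned safety result

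*Combined protocol and SAP*

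**What the plan says.** **Analysis.** Section 9.6, under safety and tolerability: "Adverse events of grade 2 or higher will be tabulated between the arms and compared by the Fisher exact test". This is the only AE analysis in section 9.6. It states no rows by event type and no all-grade summary.

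**Success criterion.** Section 9.5.2: "The safety of the TARA intervention will be demonstrated if < 15% of the participants experience a grade 2 (moderate) or grade 3 (severe", restricted to events related to TARA. Section 7.1 says the same.

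**Safety-review trigger.** Section 9.4: "If 15% of the enrolled study participants experience a Grade 2 (moderate) or Grade 3 (severe) adverse event (AE", again restricted to related events.

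**Expected harms.** Section 7 introduces them thus: "we have included the following alphabetical list of expected adverse experiences for the TARA study intervention". The list has two items. The first is "Experiencing difficult emotions such as sadness or anger during some of the TARA intervention class activities or home assignments". The second is restlessness, of which section 7 says: "If participants experience restlessness, they can stop the activity and speak to the class leader or study staff".

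**Collection.** Section 7.2 says that at each TARA visit "any and all adverse events will be collected and recorded using the Adverse Event form". Section 9.5.2 adds: "Adverse events will be collected at each visit and graded, and their attribution to their participation will be assessed". Neither sentence sets a severity floor.

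**Oversight.** Section 7.3 sends all other AEs to the funder and the Independent Monitors in an annual summary. Table A (sections 7.4 and 10.3.5) adds monthly, semi-annual and annual review of AEs and their rates, with no grade cut.

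**The concern.** The plan names the harms it expects from TARA and provides for recording, grading and attributing them. It then has no analysis that states how often they occurred. A recorded mild case falls below the cut. A moderate or severe case is counted, but nothing requires it to be shown under its own heading.

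Testing safety is part of the trial's design statement (section 3). Section 9.4 says that the trial leads to a decision on a follow-on study in depressed adolescents, where the frequency of sadness provoked by the training would be of direct interest. As the plan stands, the final report could show a nearly empty AE table and a met safety criterion, with no estimate of how often the two listed harms were recorded.

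**Working it through.** **1. Which planned safety figures can a grade 1 event enter?**

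| Planned figure | Section | Grades counted | Contribution of a grade 1 event |
|---|---|---|---|
| Fisher comparison between arms | 9.6 | 2 or higher | 0 |
| Under-15% safety criterion | 7.1, 9.5.2 | 2 or 3, related | 0 |
| 15% safety-review trigger | 9.4 | 2 or 3, related | 0 |

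The tolerability measure (CSRS) asks about feeling listened to, the importance of the content, liking the session and overall experience. The SDQ compares baseline with 12 weeks. Neither counts episodes of distress or restlessness during classes or home practice.

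**2. Inputs for an illustration.** There are 50 participants per arm (section 9.1). The plan's sample size reproduces: for d = 0.6, two-sided alpha 0.05 and power 80%, the two-sample t calculation gives 44.6, rounded up to 45, and 45/0.9 = 50. That calculation concerns putamen node strength. The safety analysis has no sample-size figure, and the documents give no AE rates or mild shares. All event counts and rates below are assumptions.

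**3. Fixed counts.** Suppose one TARA participant has a grade 2 event and x others have a recorded mild, TARA-related event. The exact (Clopper-Pearson) 95% limits for x of n are the 0.025 quantile of Beta(x, n − x + 1) and the 0.975 quantile of Beta(x + 1, n − x), with n = 50.

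| | Count | Share | Exact 95% CI |
|---|---|---|---|
| Shown by the planned table in every case | 1/50 | 2% | 0.05 to 10.6% |
| Left out if x = 5 | 5/50 | 10% | 3.3 to 21.8% |
| Left out if x = 10 | 10/50 | 20% | 10.0 to 33.7% |
| Left out if x = 20 | 20/50 | 40% | 26.4 to 54.8% |

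**4. Assumed rates.** Expected TARA participants in an all-grade table = 50 × any-grade rate. Expected in the planned table = 50 × any-grade rate × (1 − mild share). With mild shares of 70% to 90%:

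| Any-grade rate | All grades | Grade 2 or higher |
|---|---|---|
| 10% | 5 | 0.5 to 1.5 |
| 20% | 10 | 1 to 3 |
| 30% | 15 | 1.5 to 4.5 |
| 40% | 20 | 2 to 6 |

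If every case is grade 1, the planned table shows 0 at any rate.

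**5. How complete would the grade 1 data be?** Under section 7.3, AEs are solicited by one CORS question, asked at every TARA session, about a significant worsening in health since the last class. A negative answer ends the enquiry. Brief sadness or restlessness may not prompt a yes. In section 6.1, visits 2 to 13 are the TARA sessions, and no equivalent weekly questioning of waitlist participants is described. Sections 7.4 and 7.5 also have the investigator ask about AEs at each study visit, but this does not supply a weekly contact for the waitlist arm. Recorded mild events are therefore best read as a lower bound, and probably a looser one in controls.

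**The case against.** The strongest case against the point has four parts.

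*Elicitation loses mild cases before the grade cut does.* This stands. The counts in step 3 assume that the events were recorded, and an all-grade table without a caveat could give false reassurance. It is a reason to label the table, not to leave out what was recorded.

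*A grade 2 floor is defensible for a comparison between arms, because mild events are ascertained unequally.* This also stands. A reader might infer that the Fisher test should move to all grades. The documents do not support that, since the described solicitation is tied to TARA sessions.

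*Section 9.6 is silent on table rows and does not say that event types are pooled.* Correct. The defensible statement is that no summary by type is specified. The grade cut, by contrast, is written.

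*Other routes cover the concern.* Partly. A net worsening in emotional problems could show on the SDQ, and the monitors and the funder see all AEs. A reader might infer that mild harms go unrecorded or unreported; sections 7.2, 7.3 and Table A show otherwise. However, those are oversight reports with no layout by arm or event type, and nothing makes them part of the trial's result.

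**Conclusion.** The point holds in a limited form. Recorded grade 1 cases of difficult emotions and restlessness contribute zero to all three planned safety figures, and section 9.6 specifies no summary by event type. This follows from the text and needs no assumption about rates.

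The size is unknown. The illustration (1/50 shown, with 5 to 20 of 50 left out) rests on assumed counts and on those events having been recorded.

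Two stronger inferences are not supported. One is that the safety result decides the follow-on study: the go/no-go criteria in section 1.1 are effect size and retention, safety is listed among the other outcomes in section 9.5.2, and section 9.4 says only that the trial leads to the decision. The other is that most expected harms will be mild: section 7 describes the risk as very minimal but gives no severity distribution. This is an inexpensive improvement to reporting, not a flaw in the primary analysis.

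**What to change.** Keep the grade 2 or higher Fisher comparison, stating that it counts participants with at least one such event. Leave the 15% criterion unchanged. Add to section 9.6:

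> The number of participants with at least one AE will be tabulated by maximum grade (all grades) and relatedness, with separate rows for difficult emotions and restlessness and with exact 95% confidence intervals for the TARA arm. The waitlist arm will be shown descriptively only. Counts of mild events are a lower bound and are not comparable between arms, because AEs are solicited at TARA sessions by a question about significant worsening and no equivalent weekly solicitation is described for waitlist participants.

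The cost is a short addition to section 9.6 and one extra table from the existing AE forms. The safety summary will look less clean. The table can only be as complete as the elicitation behind it.

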10. DATA COLLECTION AND QUALITY ASSURANCE

10.1 Data Collection Forms

Information for each participant will be collected using the following forms and procedures:

- o Informed Consent Form (will be obtained and signed by RA via DocuSign)
- Medical History Form (source document, will be collected and signed by RA via DocuSign)
- o Inclusion/Exclusion criteria form (source document, will be filled out and signed by RA via DocuSign)
- Enrollment/Randomization form (source document, will be filled out and signed by RA via DocuSign)
- o MRI screening form (will be signed by the MRI technician. Not a source document.)
- o MRI brain scan (will be performed using a 3T MRI scanner)
- o Demographics assessment (will be performed electronically in Qualtrics)
- SDQ assessment (will be performed electronically in Qualtrics)
- Baseline Visit Checklist (source document, will be filled out and signed by RA via DocuSign)
- Child Session Rating Scale (CSRS) (source document, will be collected and signed by RA)
- Child Outcome Rating Scale (CORS) including the question: "Has there been any significant unfavorable change in your mental or physical health since last class?" (will be collected by RA. Not a source document.)
- o Adverse Events (source document, if the answer is Yes to the question above in CORS, this form will be filled out and signed by RA via DocuSign)
- Serious Adverse Events (source document, if answered Yes to the SAE question in the Adverse Event form, this form will be filled out by RA, signed by PI via DocuSign)
- o On Study Visit Checklist Form (source document, will be filled out and signed by RA via DocuSign)
- Study Completion form (source document, will be filled out by RA, signed by PI via DocuSign).

All source documents will be signed and stored electronically in DocuSign. Any data, forms, reports, video recordings, and other records that leave the site will be identified only by a participant identification number (Participant ID, PID) to maintain confidentiality. All computer entry and networking programs will be done

using PIDs only. Information will not be released without written permission of the participant, except as necessary for monitoring by the UCSF IRB, the NCCIH, and the OHRP.

10.2 Data Management

It is a single-site study; therefore, the site of operation and the Data Management Center are the same site. All the data collection described in the previous section, as well as the statistical analysis of the data will take place at UCSF.

The data collection forms that will be used in the present study are listed and described above (please see Sections 6.1, 6.2, 6.2.2, 6.2.4, 6.2.5, and 7.3).

10.3 Quality Assurance

10.3.1 Training

RAs will be training directly by the study PIs, who will also be available for questions. [name] [name] will conduct annual teacher training for the facilitators of TARA and monitor treatment fidelity using the 10-item fidelity scale (Clarke, 1998), as described in the section 10.3.5. Monitoring below.

10.3.2 Quality Control Committee

In addition to the Independent Monitor [name], one of the RAs will be appointed as the Internal QA Reviewer.

The reports that [name] will review are specified above in Table A (please see Section 10.3.5 below, Table A).

10.3.3 Metrics

Primary outcome measure: Putamen structural node strength. In our recent published study (Yuan et al., 2019), we demonstrated that diffusion MRI connectome methods can provide reliable and precise network measures, including the node strength, in adolescents.

Secondary outcome: Emotional problems measured with the Strengths and Difficulties Questionnaire (SDQ). The SDQ was selected because it is widely used in adolescents to measure internalizing problems and has good psychometric properties (Goodman, 2001).

10.3.4 Protocol Deviations

The PIs will use the NCCIH Protocol Deviation Tracking Log form (see Appendix) with the following protocol deviation code, to monthly record any and all protocols deviations.

Protocol Deviation Codes:

- A Consent Procedures
- B Inclusion/Exclusion Criteria
- C Concomitant Medication/Therapy

- D Laboratory Assessments/Procedures
- E Study Procedures
- F Serious Adverse Event Reporting/Unanticipated Adverse Device Effect
- G Randomization Procedures/Study Drug Dosing
- H Visit Schedule/Interval
- I Efficacy Ratings
- J Other

Protocol deviations will be recorded in the tracking log as they occur, to ensure completeness and accuracy of the data.

For each deviation the PIs will determine whether the deviation meets IRB and NCCIH reporting requirements.

The PIs will sign each form after it has been completed or immediately prior to a monitoring visit. If it has been signed with fewer than five deviations entered into it, the next identified deviation will be reported on a new page to ensure that all deviations have been reviewed by the PIs.

Each page will be numbered, and the log will be maintained in the Essential Documents Binder, behind the Protocol Deviations tab. The pages will be stored in reverse chronological order, with the newest pages of the log placed at the front of the section. At the conclusion of the study, the final page of the log will be identified by checking the box in the footer.

10.3.5 Monitoring

In addition to the Independent Monitors, one of the RAs will be appointed as the Internal QA Reviewer. The monitoring of protocol compliance and data quality will be conducted in accordance with Table A below.

Table A

Data type	Frequency of review	Reviewer
Subject accrual (including compliance with protocol	Monthly	PIs, Internal QA Reviewer
enrollment criteria)	Semi-annually	Independent Monitors
Status of all enrolled subjects, as	Monthly	PIs, Internal QA Reviewer
of date of reporting	Semi-annually	Independent Monitors
Data entry quality control checks on 100% of charts	Weekly	QA Reviewer
Adherence data regarding study	Monthly	PIs, Internal QA Reviewer
visits and intervention	Semi-annually	Independent Monitors
AEs and rates (including out-of-	Monthly	PIs, Internal QA Reviewer
range lab values)	Semi-annually	Independent Monitors

	Annually	NCCIH
SAEs (unexpected and related)	Per occurrence	PIs, Independent Monitors NIH/NCCIH
SAEs (expected or unrelated)	Per Occurrence	PIs, Internal QA Reviewer
	Annually	Independent Monitors, NIH/NCCIH
Unanticipated Problems	Monthly	PIs, Internal QA Reviewer
	Per Policy	IRB

In addition to the monitoring described in Table A above, [name] will monitor treatment fidelity using the 10-item fidelity scale (Clarke, 1998). For that purpose, all group sessions will be audio-recorded; the research consent process will include consent to audio record groups to facilitate treatment fidelity coding. A random sample (20%) of group sessions will be rated by [name] for adherence to the training manual and facilitator competence using the 10-item fidelity scale.

11. PARTICIPANT RIGHTS AND CONFIDENTIALITY

11.1 Institutional Review Board (IRB) Review

This protocol and the informed consent document (please see Appendix) and any subsequent modifications will be reviewed and approved by the UCSF IRB committee responsible for oversight of the study. The consent form is separate from the protocol document and included in the Appendix. Two versions of consent form are available: for 14-17-year-old participants and for 18-year-old participants.

11.2 Informed Consent Forms

A signed consent form will be obtained from each participant. For participants who cannot consent for themselves, such as those who are under the age of 18 years (e.g., minor), the parent or legal guardian of the participant who is a minor must sign the consent form. The consent form will describe the purpose of the study, the procedures to be followed, and the risks and benefits of participation. An electronic DocuSign copy will be given to each participant who is at least 18 years old and to the parent or legal guardian for each participant who is under 18 years old, and this fact will be documented in the participant's record. Participants 18 years old will sign the consent forms themselves since they are legally considered adults.

11.3 Participant Confidentiality

Any data, forms, reports, video recordings, and other records that leave the site will

be identified only by a participant identification number (Participant ID, PID) to maintain confidentiality. All records will be kept in a locked file cabinet located within a locked room that is within a locked building with 24 hours security surveillance cameras and 24 hours security personnel guarding and patrolling the locked building to ensure that the records will be kept safe and not stolen. All computer entry and networking programs will be done using PIDs only. Information will not be released without written permission of the participant, except as necessary for monitoring by the UCSF IRB, the NCCIH, and the OHRP.

